The purpose of this research project is to reduce mental health disparities for racial/ethnic and linguistic minorities by establishing community-ACO-academic partnerships to collaborate in building capacity for mental health care; training Community Health Workers (CHWs) to provide an integrated, evidence-based intervention in community settings linked to ACOs; and addressing participants' activation and social needs through a care manager that connects participants to needed services. We propose a model that includes CHWs as mental health providers, who offer an evidence-based mental health intervention called Strong Minds-Strong Communities to address the shortage of trained providers who can offer culturally congruent mental health service in non-English languages in Medicaid-based ACOs, thereby expanding ACO infrastructure and increasing access to and quality of mental healthcare for racial/ethnic and linguistic minorities in North Carolina (NC) and Massachusetts (MA).

The following protocol focuses on Aim 2, the clinical trial portion of the study.

III. Study Design Summary

A. Inclusion/Exclusion Criteria

Inclusion Criteria: Latino, Asian, Black (African American or Afro-Caribbean), or non-Latino White adults 18+ years of age with moderate to severe symptoms of depression and anxiety. This includes participants who score 50+ on the CAT-MH depression administered in English/42+ for the CAT-MH depression administered in Spanish or Chinese and/or 51+ for the

CAT-MH anxiety administered in English /41+ for the CAT-MH administered in Spanish or Chinese; and/or a positive score on the CAT-MH Major Depressive Disorder, and without any mental health care (therapy sessions with psychiatrist, psychologist or social worker) in the past 3 months or upcoming in the next month. Participants must speak English, Spanish, Mandarin, or Cantonese.

Exclusion Criteria: Participants will be excluded if there is evidence of: (1) history of psychosis, mania, or psychotic symptoms; (2) specialty mental health treatment within past 3 months; (3) upcoming behavioral health appointment (pharmacological not excluded); (4) evidence that the participant lacks capacity to consent (measured by a validated screener); (5) evidence of current suicidal risk or harm to others (affirmative responses on Paykel suicide questionnaire); and (6) severe alcohol or substance dependence (CAT score 70+, showing a high level of risk in substance use).

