Moderators. In Goal 2, race and ethnicity will be used as a moderator of the main independent variable (intervention condition). Using self-reported information, participants will be classified into four mutually exclusive categories: Latinx, non-Latinx Black, Asian, and non-Latinx White. In Goal 3, language will be used as a moderator of the main independent variable (intervention condition). Using self-reported information, participants will be classified into four mutually exclusive categories: English, Spanish, Mandarin, and Cantonese. In Goal 4, the site of recruitment will be used as a moderator of the intervention condition. Participants will be classified into two mutually exclusive categories of place of residence: North Carolina or Massachusetts.

Endpoints. The primary endpoints will be change from baseline in depression and anxiety symptoms, level of functioning, and perceived quality of care at month 6 (end of intervention) and at month 12 (6-months post-intervention). The key secondary effectiveness endpoints will

be the change from baseline in the score on the CAT-MH depression (range 0 to 100 with higher scores indicating worse depression symptoms) and the CAT-MH anxiety (range 0 to 100 with higher scores indicating worse anxiety symptoms) at month 6 and 12. The primary and key secondary effectiveness endpoints will be also evaluated in prespecified subgroup analyses based on participant's race and ethnicity, language, and site. Other exploratory endpoints will include changes from baseline in HSCL-25, WHODAS 2·0, PoC-OP, CAT-MH depression, and CAT-MH anxiety scores at month 3, about midway through the intervention. Finally, the primary and key secondary effectiveness endpoints will be evaluated in exploratory subgroup analyses based on the participant's baseline severity of depression and anxiety.

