Statistical Analyses. A two-sided P value of 0·05 will be used to calibrate the significance and false discovery rate. For the primary and key secondary endpoints, we will employ a Benjamini-Hochberg step-down procedure to adjust for the multiple comparisons across 5 outcome scores (HSCL-25, WHODAS 2·0, PoC-OP, CAT-MH depression, and CAT-MH anxiety) at 2 follow-up points (months 6 and 12). If the lowest of the ten P values was less than 0·005 (0·05 ÷ 10), it will be considered to be significant; the second lowest P value will be considered to be significant if less than 0·0056 (0·05 ÷ 9); the third lowest P value will be significant if less than 0·006 (0·05 ÷ 8); and so on. Primary and key secondary efficacy endpoints will be separately analyzed using a general linear model to estimate the treatment effect. Except for PoC-OP, baseline outcome scores will be included as covariates in all analyses. Site (Massachusetts versus North Carolina) will also be included as covariate in all analyses. This general linear model has the following form:

$$y_{i,post-baseline} = \alpha_0 + \alpha_1 Intervention_i + \alpha_2 y_{i,baseline} + \alpha_3 site_i + \varepsilon_i$$

where $y_{i,post-baseline}$ represents an outcome measure for participant i at either 6- or 12-months post-baseline. $Intervention_i$ will be an effect-coded variable equal to -0.5 if participant i was randomized to the control group and equal to 0.5 if participant i was randomized to the intervention group. $y_{i,baseline}$ is the baseline measure of the outcome (except for PoC-OP), $site_i$ is a binary indicator equal to one if participant i was recruited in Massachusetts and equal to 0 if recruited in North Carolina, and ε_i is an error term. Because participants will be recruited in multiple CBOs/clinics across the two sites, in sensitivity analyses we will use generalized linear mixed models with a random intercept accounting for clustering within CBOs/clinics for each primary and key secondary effectiveness endpoint.

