We will conduct analysis of missing data at either endpoint (primary or exploratory) to test whether that, conditional on the observed baseline variables (including baseline outcome scores), the missing at random assumption is plausible. Missing data for all statistical models (primary and key secondary endpoints, exploratory endpoint, prespecified subgroup analyses and exploratory subgroups analyses) will be handled using model-based imputation. For example, missing values to analyze change from baseline in HSCL-25 scores at the 6-month endpoint will be imputed using a general linear model where HSCL-25 scores at month 6 will be the dependent variable. An effect coded variable for intervention condition, HSCL-25 scores at baseline, and a binary indicator for site (Massachusetts versus North Carolina) will be included as predictors. The model further will also include the auxiliary baseline variables associated with missingness (e.g., participant's age or gender). The same model-based imputation will be employed for all primary and key secondary endpoints, and the exploratory endpoint. Imputation models for subgroup analyses (prespecified and exploratory) will add the moderator and its interaction with intervention condition as predictors. For each model, 20 imputed datasets will be generated. Analyses of imputed data will use Rubin's rules to obtain pooled estimates and their standard errors.

C. Power Analysis (e.g., sample size, evaluable subjects, etc.)

The proposed study aimed to recruit 1,200 participants equally distributed across sites (North Carolina and Massachusetts) and intervention conditions (Intervention and Control). That is $N = 600$ intervention participants (300 in North Carolina and 300 in Massachusetts) and $N = 600$ enhanced usual care participants (300 in North Carolina and 300 in Massachusetts).

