The target sample size was designed to achieve adequate power for our research questions. Using data from prior studies on the effectiveness of similar interventions, the estimated effect size for the outcomes ranged from 0·24 to 0·68. The nonparticipation rate of enrolled participants was assumed to be 13%. Our sample size of 1,200 (600 treatment and 600 control) from North Carolina and Massachusetts is thus effectively 1044. This sample yielded 87% power to detect an intervention effect size of 0·20, with a two-sided significance level of 0·05. Testing whether there is a differential effect of Strong Minds-Strong Communities based on participants' race and ethnicity means trying to determine whether race and ethnicity moderated the impact of the intervention. The racial and ethnic composition of our sample was roughly 63% Latinx, 14% non-Latinx Black, 13% Asian, 9% White, and 1% other races or ethnicities. Assuming a large effect size of the intervention for White participants ($> 0\cdot5$), a small effect size for Black participants ($< 0\cdot3$), and a medium effect size for Asian and Latinx participants ($> 0\cdot3$ and $< 0\cdot5$), we will have 80% power to detect a significant intervention effect in each racial and ethnic group with a sample size of 1044. Similarly, testing whether there is a differential effect of Strong Minds-Strong Communities in North Carolina compared to Massachusetts means testing whether site moderated the impact of the intervention.

VIII. Risks and Discomforts

A. Psychosocial (non-medical) risks:

The safety of intervention participants will be closely monitored during the Strong Minds-Strong Communities intervention. Participants will be administered the PHQ-9 depression screener and the GAD-7 anxiety screener during research interviews and biweekly during intervention sessions, and in biweekly check-ins for usual care participants. If participants endorse the Item

9 suicidality question of the PHQ-9, they will be administered the Paykel Suicidality Screener.

Those who endorse questions 4 and 5 of the Paykel, suggesting active suicidality, will be provided emergency care following emergency protocol developed by the research team.

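### The HSCL-25, WHODAS 2.0 and CAT-MH models adjust only for their own baseline and site, and the PoC-OP models for site alone; prespecifying the four baseline scores already collected could add modest precision at almost no cost

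*Combined protocol and SAP*

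**What the plan says.** The primary endpoints are set out under Endpoints in section VII.A: "The primary endpoints will be change from baseline in depression and anxiety symptoms, level of functioning, and perceived quality of care at month 6", and again at month 12. That makes three outcomes (HSCL-25, WHODAS 2.0, PoC-OP) at two times, or six primary endpoints. The key secondary endpoints are CAT-MH depression and CAT-MH anxiety at the same two times.

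The covariate rule under Statistical Analyses is "Except for PoC-OP, baseline outcome scores will be included as covariates in all analyses", followed by "Site (Massachusetts versus North Carolina) will also be included as covariate in all analyses". The equation has terms for intervention, one baseline score and site. The note beneath it says that the baseline term "is the baseline measure of the outcome (except for PoC-OP" again being the stated exception.

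Further baseline variables appear only in section VII.B, Missing data. There the imputation model also takes in "auxiliary baseline variables associated with missingness", with age and gender as examples. The worked HSCL-25 example names only intervention, baseline HSCL-25 and site as certain predictors.

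On timing, section V.A places randomisation after the baseline interview, and section III.A uses CAT-MH scores at screening. HSCL-25, WHODAS 2.0 and CAT-MH are all to be analysed as change from baseline, so a pre-randomisation value of each is planned.

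**The concern.** Four baseline measures of symptoms and function will be in hand, and each outcome model uses at most one of them. There is reason to think that the others carry information. Section III.A admits people on depression scores, anxiety scores "and/or a positive score on the CAT-MH Major Depressive Disorder", while the HSCL-25 total averages 10 anxiety items with 15 depression items. Two participants with the same baseline total can therefore have different symptom profiles, and the HSCL-25 model treats them alike. The plan itself proposes exploratory subgroups by baseline severity of depression and anxiety.

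PoC-OP has the most room for improvement, because its model contains no baseline score at all. The imputation rule has a similar gap: a variable enters if it relates to missingness, but a good predictor of the outcome that is unrelated to missingness is not guaranteed a place.

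What is at stake is the width of the confidence intervals, not the validity of the tests.

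**Working it through.** **Inputs from section VII.C.** The plan states: "Our sample size of 1,200 (600 treatment and 600 control) from North Carolina and Massachusetts is thus effectively 1044". It assumes 13% nonparticipation, an effect size of 0.20, two-sided alpha 0.05 and 87% power. The strictest multiplicity step in section VII.A is 0.005.

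**The plan's own figures.** 1,200 × (1 − 0.13) = 1,044, or 522 per arm, which reproduces. The unadjusted standard error in SD units is √(2/522) = 0.0619, so 0.20/0.0619 = 3.23. Subtracting 1.96 gives 1.27, which is 89.8% power. The printed 87% is not reproduced; it is somewhat conservative for its stated inputs. Covariate adjustment does not explain the gap, since it raises power further. The present point does not rest on that figure.

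**Gain from one added score.** The documents give no correlations, so all values here are assumptions. Let r1 be the correlation of the outcome with its own baseline, r2 with another baseline score, and r12 between the two baselines.

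- R² = (r1² + r2² − 2·r1·r2·r12) / (1 − r12²)
- Cut in residual variance = 1 − (1 − R²)/(1 − r1²)

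With r1 = 0.5 (own-baseline R² = 0.25) and r2 = 0.4:

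| r12 | R² | Cut in residual variance | Cut in SE | Equivalent extra participants of 1,044 |
|---|---|---|---|---|
| 0.5 | (0.41 − 0.20)/0.75 = 0.280 | 1 − 0.720/0.75 = 4.0% | 2.0% | about 44 |
| 0.6 | (0.41 − 0.24)/0.64 = 0.266 | 1 − 0.734/0.75 = 2.1% | 1.0% | about 22 |
| 0.7 | (0.41 − 0.28)/0.51 = 0.255 | 1 − 0.745/0.75 = 0.7% | 0.3% | about 7 |

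The gain is exactly zero when r2 = r1 × r12. For example, r1 = 0.5, r12 = 0.6 and r2 = 0.3 give R² = (0.34 − 0.18)/0.64 = 0.25, which is no better than own baseline alone.

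**Gain from three added scores.** With the same r1 and r2, and correlations of 0.6 among the added scores, the added R² is 0.047, 0.027 and 0.010 for r12 = 0.5, 0.6 and 0.7. Divided by 0.75, these are cuts in residual variance of about 6.2%, 3.6% and 1.4%.

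**What this does to power** (522 per arm, effect 0.20, r1 = 0.5):

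| Model | R² | Alpha 0.05 | Alpha 0.005 |
|---|---|---|---|
| No baseline score | 0 | 89.8% | 66.4% |
| Own baseline | 0.25 | 96.2% | 82.2% |
| Own baseline plus added R² of 0.03 | 0.28 | 96.8% | 84.2% |
| Own baseline plus added R² of 0.05 | 0.30 | 97.1% | 85.4% |

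**PoC-OP** (site effect ignored). If baseline symptoms and function explained 0%, 1% or 5% of its variance, power at 0.05 would be 89.8%, 90.1% or 91.2%, and the SE would fall by 0%, 0.5% or 2.5%. Nothing in the documents indicates which of these applies.

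**Price if the scores predict nothing.** The expected loss is of the order of 3/1,040 = 0.3% of variance, or 4/1,040 = 0.4% for PoC-OP.

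**The case against.** The strongest reply is that nothing is wrong. Adjustment for own baseline and site, fixed in advance, is a valid analysis of a randomised trial, and parsimony is a legitimate choice. Own-baseline adjustment already takes most of the available gain: at alpha 0.05 and r1 = 0.5 it moves power from 89.8% to 96.2%, and the further scores add about one point at most in the table above. All of this stands, and it limits the point to an optional gain in efficiency.

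A reader might infer that precision is being lost on every primary endpoint. The documents do not support that. They give no correlations, the gain can be zero, and nothing shows that symptoms or function predict perceived quality of care. A reader might also expect a cut in variance as large as 14.3% (r1 = 0.4, r2 = 0.5, r12 = 0.5: R² = 0.28, and 1 − 0.72/0.84). That case requires a different instrument to predict the outcome better than the outcome's own baseline does. With all three correlations at 0.5 the cut is 11.1%, and the more ordinary values above give much less.

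Two features may weaken the CAT-MH terms. Section III.A uses different CAT-MH cut-offs by language (50+ in English against 42+ in Spanish or Chinese for depression; 51+ against 41+ for anxiety), so one linear term across languages may be less prognostic. CAT-MH scores also determine eligibility, which may restrict their range. Both limit the gain, but neither biases the treatment effect.

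It can also be said that the imputation rule already allows other baseline scores in, since age and gender are only examples. That is true, but only for scores found to relate to missingness. Finally, the covariate sentence read alone could mean that all baseline scores enter every model. The equation and the imputation example both show one baseline score, so the narrower reading is the one that the plan specifies.

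**Conclusion.** The point holds as a free improvement, not as an error. Four of the six primary endpoints (HSCL-25 and WHODAS 2.0) and the four key secondary endpoints are adjusted for own baseline and site only. The other two primary endpoints (PoC-OP) are adjusted for site only. The analysis as planned is unbiased and has no type I error problem.

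Under the assumed correlations (0.5 own, 0.4 other, 0.5 to 0.7 between baselines), one added score would cut residual variance by about 0.7% to 4%, or roughly 0.3% to 2% of the standard error. Outside those values the gain can be zero. For PoC-OP the size is unknown. A change in the trial's conclusion is unlikely to depend on this; the case for acting is that the data are already planned and the price is negligible.

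**What to change.** Before outcomes are seen by arm, amend the equation in section VII.A to include a fixed list of baseline covariates in every primary and key secondary model, PoC-OP included: HSCL-25, WHODAS 2.0, CAT-MH depression and CAT-MH anxiety, alongside site. For HSCL-25, WHODAS 2.0 and CAT-MH, the outcome's own baseline is already one of the four; for PoC-OP all four are new.

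In section VII.B, put the same four scores in every imputation model whether or not they predict missingness, so that imputation and analysis models agree, and keep the existing provision for auxiliary variables.

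The cost is a short change to the analysis text, no new data, and three degrees of freedom (four for PoC-OP) out of about 1,040.

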Prespecified subgroup analyses of the primary and key secondary endpoints will be performed for participant's self-identified race and ethnicity (non-Hispanic White, non-Hispanic Black, Asian, and Hispanic or Latino), language (English, Spanish, Mandarin, and Cantonese), and site (Massachusetts and North Carolina). Subgroup differences will be tested in three omnibus interaction tests. These three interactions will be examined for 5 outcome scores (HSCL-25, WHODAS 2·0, PoC-OP, CAT-MH anxiety, and CAT-MH depression) at month 6 and month 12, which will result in 30 statistical tests ($3 \times 5 \times 2$). No adjustment for the multiple comparisons will be made, and about two statistically significant interaction tests ($P < 0.05$) are expected on the basis of chance alone.

Change from baseline in HSCL-25, WHODAS 2·0, PoC-OP, CAT-MH depression, and CAT-MH anxiety scores at the exploratory endpoint at month 3, and exploratory subgroup analyses based on participant's baseline severity of depression and anxiety will similarly be analyzed using a general linear model which included baseline scores (except for PoC-OP) and site as covariates.

B. Missing data

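### The race/ethnicity interaction tests and within-group effects rest on one residual variance across groups of about 63/14/13/9%; if spread differs by group they lose their nominal error rate, which HC3 standard errors plus group-specific imputation variance would guard against.

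*Combined protocol and SAP*

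**What the plan says.** All references are to Section VII of the combined protocol and SAP.

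- **Model (VII.A, Statistical Analyses).** "Primary and key secondary efficacy endpoints will be separately analyzed using a general linear model to estimate the treatment effect". The displayed equation has intervention, baseline score, site and one error term. It is the main-effect model, and no variance estimator is named. The only sensitivity model adds a random intercept for CBO/clinic, which does not let residual variance differ between racial or language groups.
- **Subgroup tests (VII.A).** "Subgroup differences will be tested in three omnibus interaction tests". Three moderators, five scores and two time points give 30 tests. They are not adjusted for multiplicity, and the reader is told that "about two statistically significant interaction tests ($P < 0.05$) are expected on the basis of chance alone". The interaction model is not displayed. The same linear model is implied, because its covariates are said to apply throughout and the exploratory subgroup analyses are described as done in a similar way.
- **Group sizes (VII.C, Power Analysis).** The race/ethnicity composition is "roughly 63% Latinx, 14% non-Latinx Black, 13% Asian, 9% White, and 1% other races or ethnicities". For language, "participants will be classified into four mutually exclusive categories: English, Spanish, Mandarin, and Cantonese", with no shares given.
- **Missing data (VII.B).** Outcomes are imputed from the same kind of linear model. For subgroup analyses the moderator and its interaction with arm are added. No group-specific residual variance is mentioned. Twenty imputations are pooled by Rubin's rules.

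**The concern.** With one residual variance, every group's treatment effect gets a standard error built from the same pooled SD. When one group is nearly two thirds of the sample, that SD is mainly its own. A small group that varies more gets intervals that are too narrow. A small group that varies less gets intervals that are too wide. The omnibus test inherits the error: too many false claims of differential effect in the first case, too few true ones found in the second.

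Differential effect by race/ethnicity is the second of the trial's four goals, and the power section claims 80% power for an effect in each racial and ethnic group, so both the interaction test and the within-group effects will be read. The remark about chance findings also assumes that each test runs at 5%. Nothing in the plan states, checks or relaxes the equal-variance assumption.

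**Working it through.** **Plan's own figures.** 1,200 × (1 − 0.13) = 1,044, as in "Our sample size of 1,200 (600 treatment and 600 control) from North Carolina and Massachusetts is thus effectively 1044". 30 × 0.05 = 1.5, consistent with about two chance findings. Both reproduce.

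**Inputs.** Shares of 63/14/13/9% applied to 1,044 give 658 Latinx, 146 Black, 136 Asian and 94 White, total 1,034. The 1% other is left out because the moderator has four categories. Allocation is taken as 1:1 within each group. SD ratios to the Latinx group are assumptions.

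**Within-group intervals, by formula.** With n_g/2 per arm, the true variance of the effect in group g is 4σ_g²/n_g. The model uses 4s²/n_g, where s² ≈ Σn_gσ_g² / Σn_g. Coverage of a nominal 95% interval is therefore about 2Φ(1.96·s/σ_g) − 1. It depends on the shares and not on the total N.

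- All three smaller groups at 1.2: s² = (658 + 376 × 1.44)/1,034 = 1.160, s = 1.077. Coverage is 2Φ(1.96 × 1.077/1.2) − 1 = 92.1%, an error rate of 7.9% in each of the three.
- All three at 0.8: s² = (658 + 376 × 0.64)/1,034 = 0.869, s = 0.932. Coverage is 97.8%, an error rate of 2.2%.
- Only White at 1.25: s² = (940 + 94 × 1.5625)/1,034 = 1.051, s = 1.025. White coverage is 89.2%; simulation gave 89.0%.
- Black 1.2 and Asian 0.8: s² = (752 + 146 × 1.44 + 136 × 0.64)/1,034 = 1.015, s = 1.007. Coverage is 90.0% for Black and 98.6% for Asian participants.

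**Omnibus 3-df test at nominal 5%, simulated under no effect (100,000 to 200,000 trials per setting).**

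| Assumed SD pattern (Latinx = 1) | Error rate, pooled variance |
|---|---|
| All equal | about 5% |
| Three smaller groups 1.1 / 1.2 | 6.9% / 8.8% |
| Three smaller groups 0.9 / 0.8 | 3.3% / 1.9% |
| White only 1.1 / 1.2 | 5.8% / 6.7% |
| White only 0.8 | 3.8% |
| Black 1.2, Asian 0.8 | 5.5% |
| Black 1.1, Asian 0.9 | 5.2% |

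**With HC3 (20,000 trials per setting, baseline and site in the model, complete data).** Omnibus error is 4.7 to 5.4% and coverage 94.7 to 95.2% over SD ratios 0.67 to 2. HC0 and HC1 give 5.2 to 6.0% for race/ethnicity. With equal SDs, power under HC3 against the pooled-variance test is 45.9% v 46.4% in one setting and 30.5% v 31.1% in another.

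**Language.** The shares are unknown. Assuming Cantonese speakers are 2 to 5% of the sample, the pooled-variance test runs at 8.0 to 8.7% if that group alone has SD ratio 1.25. With a group of about 20 to 25 people, HC0 and HC1 run at 6.4 to 7.1%; HC3 stays near 5%.

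**Site.** At 50:50 the interaction test stays at 4.5 to 5.3%, but site-specific intervals cover 90.3% and 98.7% at SD ratio 1.5.

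**Imputation from a common SD (1,500 trials per setting, 20 imputations, HC3).** Coverage for the White-group effect with 13% imputed is 93.7% with equal SDs and 92.9% at ratios 1.5 and 2. That gap is within simulation error: √(0.93 × 0.07/1,500) ≈ 0.7 points. With 25% imputed, coverage is 90.4% and 89.9% at those ratios, which is a clear shortfall.

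**The case against.** The strongest reply is that unequal spread is hypothetical. No SD by group is given. Features that might suggest it prove nothing about residual variance: the bounded scales apply to every group, the language-specific CAT-MH entry cut-offs concern where a threshold sits, and the differing effect sizes in the power section concern means. This stands, and the point must be put conditionally. A reader might infer that the 20 race/ethnicity and language tests will miss their nominal level; the documents do not support that.

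Second, equal ratios in all three smaller groups are an unfavourable pattern for the omnibus test. This also stands: the milder patterns above give 3.8 to 6.7%. It does not rescue the group intervals. In the Black 1.2, Asian 0.8 pattern the omnibus test is at 5.5% while the two groups' coverage is 90.0% and 98.6%.

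Third, the practical effect on the count of chance findings is small. At 8.8% for the ten race/ethnicity tests and 5% for the other twenty, the expected number is 10 × 0.088 + 20 × 0.05 = 1.9 against 1.5, so the plan's caveat remains roughly true. That limits the weight of the point, though it does not help a reader of one particular test or interval.

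Fourth, the pooled variance in the interaction model is inferred and not written. That is correct; it is the natural reading, and one sentence in the plan would settle it either way.

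**Conclusion.** The point holds conditionally. As the plan reads, nothing protects the race/ethnicity interaction tests and within-group effects if residual spread differs between groups of very unequal size. Under assumed SD ratios of 0.8 to 1.2, the omnibus test runs at about 2 to 9% if all three smaller groups differ alike, and at about 4 to 7% if only the White group does. The direction depends on which group varies more. The figures assume normal outcomes, 1:1 allocation within group and no clustering by CBO/clinic.

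Three stronger readings are not supported:

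- The 63% to 9% range does not describe language. Language is exposed only if its groups are also unequal, which the documents do not report.
- The primary arm comparison is not compromised. With 1:1 allocation its standard error rests on the average variance, which the pooled estimate gives correctly.
- Robust standard errors are not a complete or free remedy. HC3 has a small cost in power, and on its own it does not correct outcomes imputed from a common variance.

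This is a worthwhile low-cost improvement to prespecified subgroup analyses. It does not bear on the trial's main conclusion.

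**What to change.** 1. In the subgroup paragraph of Section VII.A, write out the interaction model. State that interaction tests and subgroup-specific effects use HC3 standard errors, or residual variances estimated separately by moderator group, computed in each imputed dataset and pooled by Rubin's rules. Name HC3, because HC0 and HC1 are liberal in small groups. Apply this to site as well, since site-specific intervals are exposed even though the site interaction test is not.
2. In Section VII.B, let the residual variance of the subgroup imputation models differ by moderator group, for example by imputing within group. Where a group is very small, a shared mean model with group-specific variance may be more stable. The simulations above did not test group-specific imputation; it is recommended because it removes the common-variance assumption that HC3 cannot undo.

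**Cost.** About two sentences, one software option and slightly more imputation work. If variances are in fact equal, the loss is under one point of power, with slightly wider intervals in the smallest groups. On a given dataset HC3 leaves the point estimates unchanged; group-specific variances may shift them slightly through the shared covariates.
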